"Chain vaping" is an e-cigarette use behavior identical in practice to chain smoking and is well documented in e-cig user forums. Some have described vaping an entire day, either passively or actively, as a cigarette smoker does. Some discuss vaping "hard" for 10-15 minutes, some consume 10-20 ml per day, and some advise as to maximizing battery life and coil replacement for others who chain vape (32,33). A 10 ml per day vaping habit, if consuming a product that is 20% ethanol, would be inhaling as much as 1.6 g of ethanol. Vaping ethanol as a way to get drunk without the calories is also commonly debated in forums, and a cautioned activity (34). Even though inhaling ethanol happens over a longer course of time than drinking ethanol, potentially mitigating some effects of the ethanol, it is not known definitively. A single published study evaluated the impact of vaping ethanol (23.5%) on subjective drug effects, BAC, and urine ethyl glucuronide (EtG). While they allowed for both directed puffing (10 puffs) and ad lib puffing, they demonstrated zero impact to subjective drug effects, significant change in dexterity performance, and 15% of the participants had detectable EtG / EtS in the urine after ad lib puffing (no plasma ethanol was detected after the 10-puff use period). They concluded that increased risk may be an issue with vaping ethanol without a subject aware of his/her level of impairment (18). Limitations to this study include (i) participants were allowed to ad lib vape, meaning that the investigators were unable to record how much ethanol was consumed in each puff; (ii) they did not use impairment techniques relevant to or understood by law enforcement (i.e. Standardized Field Sobriety Test), and (iii) the dexterity performance conclusion could be the result of a learned performance as opposed to being impacted by impairment. It was also not demonstrated in the manuscript that they evaluated the wait period between vaping and the preliminary breath test.

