**4. \* Describe the scientific benefit or importance of the knowledge to be gained:**

The benefits of this research are of a scientific nature, which will specifically inform and potentially impact the criminal justice sector in addition to the general societal understanding of the effects of ECIGs. In particular, the use of ECIGs has become increasingly popular, with some liquids containing ethanol. There is significant lack of information about ECIGs and vaping ethanol. It is not known if vaping ethanol will impact the field sobriety test performed at DUI stops. It is not known if vaping ethanol will impact the tests measuring impairment by the walk-and-turn, the one-legged stand, or horizontal gaze nystagmus. Additionally, it is not known if vaping will interfere with the breath test, which requires a 15-20 minute observed wait period before blowing into the device. The results of this study will inform criminal justice practice, to include court testimony, and policing protocols. It will also inform future work regarding the physiological and subjective effects of ECIG use in e-cigarette users.

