Participants will be asked to abstain from food 2 hours prior to arrival and ethanol 24 hours prior to arrival. Each session will begin with a 60-minute waiting period (to be sure that participants have not eaten prior to assessments, which can interfere with testing). Pregnancy (via urine), drug (via urine), and breath alcohol concentration (BrAC via probationary breath test or PBT, which involves blowing through a tube) will be confirmed negative prior to each session. The session will then commence with insertion of a venous catheter and a reading of heart rate and blood pressure.

Then, subjective measures will be completed (BAES, SHAS, DEV, LHS, and GLMS questionnaires, and several questions about driving and memory, see attachments). Next, baseline blood, breath, and oral fluid samples will be collected. Also, a Standardized Field Sobriety Test (horizontal and vertical gaze nystagmus with the DAX recording device, walk-and-turn, one-legged stand; see documents for the SFST procedures) will be conducted by a trained, plain-clothed VCU police officer.

Participants will drink the placebo ethyl alcohol (EtOH) drink or 20% EtOH drink within 10 minutes. Blood, urine, oral fluid, and breath will also be collected at pre-determined intervals for 300 minutes. Participants will vape 10 times with 4-second puffs 45 minutes after the beverage is consumed. Participants will be asked to take additional puffs from the e-cigarette toward the end of the elimination period, at 240 minutes.

During puffing, equipment will be used to measure puffs (puff topography). The equipment consists of a mouthpiece that is attached to the e-cigarette, which is attached to tubing that is attached to a box and computer that measures aspects of puffing. We have used this equipment in many previous studies.

At the end of each session, participants will be offered snacks before leaving (i.e., granola bars, chips, juice, and similar). Participants will be released at a time point in which the BAC will be <0.05 g%.

In the event that the venous catheter stops working and only one additional sample is needed (sample #6), venipuncture may be used instead of placing a new catheter for one sample, as in this case, venipuncture will be more comfortable for the participant. On any given session, there will still be no more than 3 "sticks" permitted, including for catheter insertion and for venipuncture.

Experimental session timeline (times approximate):

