Participant arrives, pregnancy test, drug test, CO, BrAC test, BP and HR reading  
-60 waiting period  
-30 Catheter Insert  
-10 Questionnaires  
0 min Baseline Blood (B), Breath (Br), Oral Fluid (OF), and SFST  
15 min Drink first 1/2 of beverage  
25 min Drink second 1/2 of beverage  
35 min B, OF  
40 min OF  
45 min Br  
55 min OF, Br, SFST  
75 min B, OF, Br  
85 min Vape 10x 4-seconds  
90 min B, OF, Br, SFST, questionnaires  
125 min Br  
155 min Br  
200 min Br  
235 min B, OF, Br  
245 min Vape 10x 4-seconds  
250 min B, OF, Br, SFST, questionnaires  
280 min OF, Br  
310 min Br, Urine (BAC must be <.05 g% before participant can leave), BP and HR reading

Please note that if a participant belches before the PBT breath test is scheduled to be administered, the session may be prolonged, as belching can interfere with the PBT.

Also, if participants need to use the bathroom during the session, we will ask for an additional urine sample at that time.

At the end of each session, the police officer will be asked two hypothetical questions about whether or not, if in the field, they would have made an arrest based on the results of the SFST and PBT (see questions in documents). No participants will actually be arrested.

Finally, if the study nurse has any concerns about a participant's blood pressure, we may give the participant information about blood pressure (see documents).

Transportation: Participants will be offered transportation via Uber for each session (not for the screening visit). For the sessions, participants must either have someone else drive them to and from the session, or use Uber(both ways). Study staff can schedule Uber rides for participants using our Center account, which can also be set up to communicate directly with participants. This involves Center staff entering the participant's name and phone number

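### No breath test is scheduled 15-20 minutes after vaping, so a reading raised at 5 minutes and clear by 35-40 would leave the adequacy of the observed wait undecided

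*Protocol*

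**What the plan says.** Background item 4 (scientific benefit) names several unknowns. After the field sobriety and impairment tests it adds that "it is not known if vaping will interfere with the breath test, which requires a 15-20 minute observed wait period". It then states the intended use: "The results of this study will inform criminal justice practice, to include court testimony, and policing protocols". Background item 1, discussing the one published study of vaped ethanol, remarks that its paper did not show that "they evaluated the wait period between vaping and the preliminary breath test".

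The session timeline under Study Procedures, item 6, gives the two vaping bouts and the combined assessments that follow them:

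- "85 min Vape 10x 4-seconds", then "90 min B, OF, Br, SFST, questionnaires", with the next breath test at 125 min.
- "245 min Vape 10x 4-seconds", then "250 min B, OF, Br, SFST, questionnaires", with the next breath test at 280 min.

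The timeline describes its times as approximate and gives no windows. The narrative above it places the first bout 45 minutes after the beverage is consumed and the second at 240 minutes.

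**The concern.** The protocol cites the observed wait as something not yet understood in relation to vaping, and notes that the earlier study did not show it had examined it. One would therefore expect a reading at about the moment an officer would test, once the wait has run. The schedule instead reads breath about 5 min after vaping and not again until 35 or 40 min.

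Suppose vaping raises the reading briefly. The trial would then show that interference exists and that it has gone by 35-40 min, but not whether a 15-20 minute wait removes it. That last step is what policing practice would need, and readings not taken cannot be recovered once the sessions are done.

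**Working it through.** **Inputs (session timeline).** Vaping at 85 and 245 min. Breath tests at 0, 45, 55, 75, 90, 125, 155, 200, 235, 250, 280 and 310 min: 12 in all, 11 after baseline. Those at 45, 55 and 75 precede any vaping, so 11 - 3 = 8 follow a bout.

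**Lag = breath time minus the start of the preceding bout.**

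| Bout | First test | Second test | Third test |
|---|---|---|---|
| 85 min | 90 - 85 = 5 | 125 - 85 = 40 | 155 - 85 = 70 |
| 245 min | 250 - 245 = 5 | 280 - 245 = 35 | 310 - 245 = 65 |

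The other two tests, at 200 and 235 min, come 115 and 150 min after the first bout. None of the 8 lags lies in 15-20 min.

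**Counting from the last puff.** The interval between puffs is not given. Ten 4-second puffs take at least 40 s; assume a bout lasts up to 5 min. The lags become 0-5 and 35-40 min for bout 1, and 0-5 and 30-35 min for bout 2. None lies in 15-20 min.

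**Approximate times.** To reach a lag of 15 min, the 90- or 250-min test would have to slip by 10 min. To reach a lag of 20 min, the 125-min test would have to come 20 min early, or the 280-min test 15 min early.

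**Narrative times.** The timeline starts the second half of the drink at 25 min. If it is finished at 35, bout 1 is at 35 + 45 = 80 and the lags are 10 and 45. Taking 240 min on the session clock (the narrative does not state its zero), bout 2 has lags of 10 and 40. The window is still missed. Only if the drink counts as finished at 25 would bout 1 fall at 70 and the 90-min test at 20 min. That conflicts with the timeline's 85 and helps bout 1 alone.

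**What each result would show, assuming only that any residue declines with time.**

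- No excess at 5 min: none at 15-20 min, so the wait is long enough.
- Excess still present at 35-40 min: present at 15-20 min too, so the wait is too short.
- Raised at 5, clear by 35-40: the value at 15-20 min lies anywhere between the two, so the question stays open.

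**Illustration of the third case (assumptions, not protocol figures).** Assume exponential decline, an excess E of 0.02 to 0.10 g% at 5 min, and an excess at the later test T (35 or 40 min) just under a detection limit L of 0.002 to 0.005 g%. The slowest decline compatible with a clear later test has k = ln(E/L)/(T - 5), and the largest excess at time t is E·exp(-k(t - 5)).

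- E = 0.02, L = 0.002, T = 35: k = ln(10)/30 = 0.077; at most 0.009 g% at 15 min and 0.006 at 20.
- E = 0.10, L = 0.005, T = 40: k = ln(20)/35 = 0.086; at most 0.043 g% at 15 min and 0.028 at 20.

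Faster decline would bring these values close to zero, so the same observed pattern fits a negligible and a material excess.

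**The case against.** A reader might infer that no breath test falls within the wait at all, or that the trial cannot show whether the wait is long enough. The documents support neither. The 15-20 minutes is the length of the wait, and the tests at 5 min lie inside it; what is missing is a test at its end. Because the schedule brackets the wait, two of the three possible patterns give an answer.

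A reader might also take this to be the trial's main criminal-justice question. The hypothesis and aims name breath tests, field sobriety tests, blood ethanol and biomarkers, and do not mention the wait. Background item 4 raises it as an additional point, after the sobriety and impairment tests. The literal question there is whether vaping interferes with the breath test, and readings at 5 and 35-40 min compared with the 0% device do address interference.

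Nor do the documents establish that the undecided pattern is the expected one. The Background reports no plasma ethanol after 10 puffs in the earlier study. That makes a lasting excess less likely but does not say how breath behaves at 5 min. The decay figures are assumed, and the upper starting value exceeds the protocol's 0.08 g% target. Under the same exponential model, a detectable residue at 35-40 min would permit interpolation, though only by trusting the model.

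All of this limits the size of the point. The gap at 15-20 min remains.

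**Conclusion.** The point holds as a limited design weakness. None of the 8 post-vaping breath tests is scheduled at 15-20 min, and neither the approximate times nor the 240-minute narrative time closes the gap. The trial can judge the wait if the result is clear-cut at 5 min or at 35-40 min, and cannot if readings are raised at the first and clear by the second. How likely that result is cannot be stated from the protocol.

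The three-way reading assumes that a residue only declines after vaping. The lags assume the timeline's vaping times, which differ from the narrative's. No stated aim fails without the change. It is a worthwhile and inexpensive improvement to a secondary question that the protocol raises itself.

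**What to change.** Add one breath reading 15-20 min after the last puff of each bout. On the timeline's clock this is about 105 and 265 min: 105 - 85 = 20 and 265 - 245 = 20, less a bout of up to 5 min, gives 15-20 min after the last puff. Both slots are free in the present timeline.

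Add these readings and do not move existing ones. Shifting the 125- and 280-min tests would remove the 35-40 min bracket that detects a lasting excess, and would separate the 280-min breath and oral fluid samples.

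Record the time of the last puff and of each blow. Compare each new reading with the same-clock reading from the same participant's 0%-device session with the matching beverage.

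Reconcile the vaping times in the narrative (45 minutes after the beverage, and 240 minutes) with those in the timeline (85 and 245 min), so that the lag is defined; the new readings should follow whichever times are confirmed.

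Cost: a protocol amendment and two short blows per session, raising 12 to 14, or 2 × 4 = 8 more per participant over four sessions. The schedule becomes slightly fuller; the breath test itself is already in use.
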